#### **4.3.4. Immunogenicity analysis set**

The immunogenicity analysis set is a subset of the safety analysis set and will include patients who have at least one ADA/nAb sample collected for avelumab in Arm A.

### **5. GENERAL METHODOLOGY AND CONVENTIONS**

#### **5.1. Hypotheses and Decision Rules**

##### **5.1.1. Hypotheses and sample size determination**

The study is designed to test the following hypotheses:

$$H_{01}: HR_{PFS(A/B)} \geq 1, \text{ versus } H_{a1}: HR_{PFS(A/B)} < 1$$

where  $HR_{PFS(A/B)}$  represents the hazard ratio for PFS in Arm A vs Arm B.

Approximately 640 patients will be randomized to the treatment arms using a 1:1 randomization, stratified by tumor stage (<T4 vs T4), nodal stage (N0/N1/N2a/N2b vs N2c/N3), and HPV status (positive vs negative) as measured by p16 expression by IHC.

Two hundred eight-nine (289) PFS events per modified RECIST v1.1 will be required to have at least 90% power to detect a hazard ratio of 0.68 using a 1-sided log-rank test at a

significance level of 0.025, and a 2-look group-sequential design with Lan-DeMets (O’Brien-Fleming)  $\alpha$ -spending function to determine the efficacy boundary and a Gamma Family (-7)  $\beta$ -spending function to determine the non-binding futility boundary.

The sample size for this study is determined based on the assumptions that the median PFS in Arm B is 33 months (Ang KK, et al., 2010^2; Ang KK, et al., 2014) and that combination treatment with avelumab + SOC CRT (Arm A) is expected to increase the median PFS to  $\geq$  48.5 months, corresponding to a hazard ratio of 0.68 under the exponential model assumption. The sample size further assumes a 15% drop-out rate within each treatment arm and a non-uniform patient accrual over a 22-month period. The data cut-off for the primary PFS analysis will occur after the target number of events has been reached and the last patient randomized in the study has been followed for at least 24 months after randomization.

The study will also include a formal comparison for OS. The following hypotheses will be tested according to a testing strategy that preserves the overall type I error in the study as described in Section 5.1.2:

$$H_{02}: HR_{OS(A/B)} \geq 1, \text{ versus } H_{a2}: HR_{OS(A/B)} < 1$$

where  $HR_{OS(A/B)}$  represents the hazard ratio for OS in Arm A vs Arm B.

With 392 deaths, the study will have 80% cumulative power (unadjusted for the pre-testing, in the hierarchical procedure, of PFS) to detect a hazard ratio of 0.75 using a 1-sided log-rank test at a significance level of 0.025 and a 5-look group-sequential design with Lan-DeMets (O’Brien-Fleming)  $\alpha$ -spending function to determine the efficacy boundary. If the median OS in Arm B is 70 months (Ang KK, et al., 2010^2; Ang KK, et al., 2014), a hazard ratio of 0.75 corresponds to an increase in median OS from 70 months in Arm B to 93 months in Arm A under the exponential model assumption.

Table 6 summarizes the power to detect several hazard ratios and the estimated duration of the study based on the same number of patients that are planned to be enrolled in the study to meet the primary endpoint and assuming a 5% dropout rate for survival follow-up. These calculations are conditional on achieving statistical significance for the test of PFS.

**Table 6. Power to Detect Specific Hazard Ratios for OS**

HR under $H_{a2}$	Power	Calendar time (months) to 392 deaths under $H_{a2}$
0.75	80%	127
0.80	58%	124
0.70	93%	131

Simulations performed using EAST 6.4.1 with number of simulations = 10,000 and seed=7282016.

### 5.1.2. Decision rules

To protect the integrity of the study and to preserve the type I error rate, a fraction of alpha (0.0097) for PFS efficacy will be spent at the interim analysis and accounted for in the overall type I error rate if the interim analysis is performed exactly at the planned number of

PFS events. The nominal significance levels for the interim and final efficacy analyses of PFS will be determined by using the Lan-DeMets procedure with an O'Brien-Fleming stopping boundary. The overall significance level for the efficacy analysis of PFS will be preserved at 0.025 (1-sided).

Two analyses will be performed for PFS:

- 1) an interim analysis after all patients have been randomized in the study and at least 217 (75%) of the 289 PFS events have been documented per modified RECIST v1.1, and
- 2) the final analysis for PFS after all patients randomized in the study have been followed for 24 months and at least 289 PFS events have been documented per modified RECIST v1.1.

If the value of the test statistic for PFS exceeds the efficacy boundary for a comparison ( $z < -2.338$ ,  $p < 0.010$  if the IA is performed after exactly 217 events), then superiority of Arm A compared to Arm B could be declared. If the value of the test statistic for PFS exceeds the futility boundary ( $z > -0.728$ ,  $p > 0.233$  if the IA is performed after exactly 217 events), then the study may be stopped for futility.

Since the observed number of events at the interim analysis may not be exactly equal to the planned 217 PFS events, the efficacy and futility boundaries will be updated based on the actual number of observed events using the pre-specified  $\alpha$ - and  $\beta$ -spending functions. Therefore, the observed Z-test statistic at the interim analysis will be compared with the updated efficacy and futility boundaries.

If the study continues to final analysis, the p-value that will be used to declare statistical significance at the final analysis will be based on the actual number of PFS events documented at the cut-off date for the final analysis and the  $\alpha$  already spent at the interim analysis. Therefore, if the interim analysis occurs after exactly 217 events, and the study continues until the final analysis, the observed p-value for the comparison will have to be  $< 0.022$  to declare statistical significance. If the number of events in the final analysis deviates from the expected number of events, the final analysis criterion will be determined so that the overall significance level across all analyses is maintained at 1-sided 0.025.

Based on the stopping boundaries defined above and the timing of interim analysis at 75% information fraction the design has the following operating characteristics.

**Table 7. Simulated cumulative probabilities to stop for futility at the interim or final PFS analysis**

Scenario	Look	Number of PFS events	Calendar Time (months)	P(Reject H 01 )	P(Reject H a1 )
H 01 is true (HR=1)	Interim	217	34	0.0093	0.7679
	Final	289	44	0.0246	0.9754
H a1 is true (HR=0.68)	Interim	217	38	0.6917	0.0197
	Final	289	51	0.9010	0.0990

Simulations performed in EAST 6.4.1 with number of simulations = 10,000 and seed=7282016.

The secondary OS endpoint will be analyzed using a hierarchical testing procedure, provided the primary endpoint PFS endpoint is statistically significant favoring Arm A. An  $\alpha$ -spending function according to Lan-DeMets (O'Brien-Fleming) independent of the one used for the primary efficacy analysis will be used to preserve the 0.025 overall level of significance across the hypotheses and the repeated testing of the OS hypotheses in the interim and final analyses. The trial allows for the stopping of the study for a superior OS result, provided the primary PFS endpoint has already been shown to be statistically significant favoring Arm A.

A maximum of five analyses are planned for OS:

- 1) an interim analysis at the time of the interim analysis for PFS (provided PFS is significant);
- 2) an interim analysis at the projected time of the final analysis for PFS (provided PFS is significant);
- 3) an interim analysis when 270 deaths are observed;
- 4) an interim analysis when 345 deaths are observed;
- 5) a final analysis for OS when 392 deaths are observed.

The exact nominal p-values that will need to be observed to declare statistical significance at the time of these analyses for OS will depend on the number of OS events that have been observed at the time of these analyses and the  $\alpha$  for OS already spent at the time of earlier analyses.

If OS is tested alone, independent of the testing strategy for PFS, the design concerning overall survival analyses will have the following operating characteristics. These calculations are unadjusted for the pre-testing of PFS.

**Table 8. Simulated cumulative probabilities to stop for efficacy on overall survival at PFS interim analysis, final PFS analysis, third interim OS analysis, fourth interim OS analysis, or final OS analysis**

Scenario	Look	Number of deaths	Calendar Time (months)	P(Reject $H_{0j}$ )
$H_{02}$ is true (HR=1)	Interim PFS	139	38	<0.0001
	Final PFS	198	51	0.0005
	3 rd Interim OS	270	69	0.0067
	4 th Interim OS	345	93	0.0160
	Final OS	392	112	0.0247
$H_{a2}$ is true (HR=0.75)	Interim PFS	122	38	0.0104
	Final PFS	176	51	0.1060
	3 rd Interim OS	270	78	0.4613
	4 th Interim OS	345	106	0.6973
	Final OS	392	127	0.8015
$H_{a2}$ is true (HR=0.80)	Interim PFS	126	38	0.0037
	Final PFS	181	51	0.0470
	3 rd Interim OS	270	76	0.2625
	4 th Interim OS	345	103	0.4738
	Final OS	392	124	0.5825

Interim and final PFS analyses calendar time expected at 38 and 51 months, respectively, under  $H_{a1}$  (HR for PFS=0.68).

Simulations performed in EAST 6.4.1 with number of simulations = 10,000 and randomization seed =7282016.

## 5.2. General Methods

As described in Section 3.4, in this study ‘**treatment arm**’ refers to one of the following:

- Arm A = Avelumab + SOC CRT;
- Arm B = Placebo + SOC CRT.

Endpoints will be summarized based on the analysis sets described in Table 5 by treatment arm, unless otherwise specified.

### 5.2.1. Data handling after the cut-off date

Data after the cut-off date may not undergo the cleaning process and will not be displayed in any listings or used for summary statistics, statistical analyses or imputations.

### **5.2.2. Pooling of centers**

In order to provide overall estimates of treatment effects, data will be pooled across centers. The ‘center’ factor will not be considered in statistical models or for subgroup analyses due to the high number of participating centers in contrast to the anticipated small number of patients randomized at each center.

### **5.2.3. Presentation of continuous and qualitative variables**

Continuous variables will be summarized using descriptive statistics ie, number of non-missing values and number of missing values [ie, n (missing)], mean, median, standard deviation (SD), minimum, maximum and first and third quartile (Q1 and Q3).

Qualitative variables will be summarized by frequency counts and percentages. Unless otherwise specified, the calculation of proportions will include the missing category. Therefore, counts of missing observations will be included in the denominator and presented as a separate category.

In case the analysis refers only to certain visits, percentages will be based on the number of patients still present in the study at that visit, unless otherwise specified.

Confidence intervals (CIs) may also be reported as noted in subsequent sections.

### **5.2.4. Definition of study day**

Start day of study treatment is the day of the first dose of study treatment.

The study day for assessments occurring on or after the start of study treatment (eg, adverse event onset, tumor measurement) will be calculated as:

$$\text{Study day} = \text{Date of the assessment/event} - \text{start of study treatment} + 1.$$

The study day for assessments occurring prior to the first dose of study treatment (eg, baseline characteristics, medical history) will be negative and calculated as:

$$\text{Study day} = \text{Date of the assessment/event} - \text{start of study treatment}.$$

The study day will be displayed in all relevant data listings.

### **5.2.5. Definition of start of new anti-cancer drug therapy**

Start date of new anti-cancer drug therapy is used to determine the end of the on-treatment period (see Section 5.2.7).

The start date of new anti-cancer drug therapy is the earliest start date of anti-cancer drug therapy recorded in the ‘Follow-up Cancer Therapy’ eCRF pages that is after the first dose of study treatment. When start date of anti-cancer drug therapy is missing or partially missing, the imputation rules described in Section 5.3.3.4 should be applied using only data from the ‘Follow-up Cancer Therapy’ eCRF pages.

### 5.2.6. Definition of start of new anti-cancer therapy

The start date of new anti-cancer therapy is the earliest date after randomization amongst the following:

- Start date of anti-cancer drug therapy recorded in the ‘Follow-up Cancer Therapy’ eCRF pages
- Start date of radiation therapy recorded in ‘Follow-up Radiation Therapy’ eCRF pages with ‘Treatment Intent’ = ‘Curative in intent’
- Surgery date recorded in ‘Concomitant Surgery’, and ‘Follow-up Surgery’ eCRF pages when ‘Surgery Outcome’ = ‘Resected’ or ‘Partially Resected’.

When start date of anti-cancer therapy is missing or partially missing, the imputation rules described in Section 5.3.3.4 should be applied using ‘Follow-up Cancer Therapy’, ‘Follow-up Radiation Therapy’, ‘Concomitant Surgery’, and ‘Follow-up Surgery’ eCRF pages.

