Patients that came off of protocol therapy during the CRT phase all completed SOC CRT off protocol, with the exception of a single patient who, for personal reasons, elected to stop all therapy against medical advice. For the patients who completed IMRT, the median total dose of IMRT was the protocol expected dose of 70 Gy (range: 40.0-70.0) (the individual who had 40 Gy on study completed IMRT to 70 Gy off of study). Overall AE profile was consistent with the known AE profile of CRT.

Additional information for this compound may be found in the single reference safety document (SRSD), which for this study is the avelumab investigator's brochure.

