## **8.2. Reporting Period**

For SAEs, the active reporting period to Pfizer or its designated representative begins from the time that the patient provides informed consent, which is obtained prior to the patient's participation in the study, ie, prior to undergoing any study-related procedure and/or receiving investigational product, through and including 90 calendar days after the last administration of the investigational product. SAEs occurring to a patient after the active reporting period has ended should be reported to the sponsor if the investigator becomes aware of them; at a minimum, all SAEs that the investigator believes have at least a reasonable possibility of being related to investigational product are to be reported to the sponsor.

AEs (serious and non-serious) should be recorded on the CRF from the time the patient has taken at least 1 dose of investigational product through 90 days after last administration of investigational product.

- If a patient begins a new anticancer therapy, the AE reporting period for non-serious AEs ends at the time the new treatment is started. Death must be reported if it occurs during the SAE reporting period after the last dose of investigational product, irrespective of any intervening treatment.

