**Table 2. Chemoradiation and Avelumab/Placebo Treatment Schedule**

	Lead-in Phase (7 days) a	CRT Phase (63 days)								Maintenance Phase b
	-- Day --	----- Day -----								
	1	1	8	15	22	25	29	36	39	43
IMRT (70 Gy/35 fractions/7 weeks; 1 fraction per day, 5 fractions/week [Monday – Friday])		X→	X→	X→	X	→	X→	X→	→	X→
Cisplatin (100 mg/m^2 Q3W)		X			X					X
Avelumab (10 mg/kg) or placebo	X		X		X c			X		Q2W

- Lead-in Phase to start 7 days prior to initiation of CRT Phase.
- Maintenance Phase to start after completion of the CRT Phase (ie, 2 weeks following completion of CRT) and be 12 months in duration. CRT phase may be extended as required for patient recovery from CRT; however, it is hypothesized that patients will receive maximal benefit from beginning maintenance as close to the scheduled time as possible.
- Day 25 dose of avelumab/placebo during the CRT Phase may be administered between Day 24 and Day 29. Cisplatin should be administered on a Monday or Tuesday if feasible to maximize overlap with IMRT. CRT = Chemoradiotherapy; IMRT = intensity-modulated radiation therapy; Q2W = every 2 weeks; Q3W = every 3 weeks.

The investigator will assess antitumor activity based on radiological assessments and clinical evaluation of patients using modified RECIST v1.1 at baseline, 12 weeks after the completion of CRT (ie, 10 weeks following completion of the CRT Phase of the study), every 16 weeks thereafter for 48 months (208 weeks), and every 24 weeks thereafter until confirmed disease progression per modified RECIST v1.1 and regardless of discontinuation of study treatment or initiation of subsequent anti-cancer therapy.

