**Table 12. Outcome and Event Date for PFS Sensitivity Analysis (M1)**

Scenario	Date of Progression/Censoring	Outcome
No adequate baseline assessment	Date of randomization a	Censored a
PD or death 
 
- following at most one missing or indeterminate post-baseline tumor assessment or clinical evaluation, OR
 
- ≤ 36 weeks after the date of randomization
 
	Date of PD or death	Event
PD or death following two or more missing or indeterminate post-baseline tumor assessments or clinical evaluations b	Date of last adequate tumor assessment b or clinical evaluation documenting no PD prior to new anti-cancer therapy or missed assessments	Censored
No PD and no death		
New anti-cancer therapy given		
a If the patient dies ≤36 weeks after date of randomization, the death is an event with date on death date. b If there are no adequate post-baseline tumor assessments or clinical evaluations prior to the PD or death, then the time without adequate assessment should be measured from the date of randomization; if the criteria were met the censoring will be on the date of randomization		

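### The SAP's new-therapy definitions do not exempt finishing the assigned CRT off protocol, which can remove such patients from S1, M1 and M1_B before their first scheduled scan and cut short their AE capture

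*SAP*

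**What the plan says.** **Such patients exist.** Protocol 1.2.2, reporting the first E-DMC review, states: "Patients that came off of protocol therapy during the CRT phase all completed SOC CRT off protocol", with one exception. On the reported IMRT doses it adds that "the individual who had 40 Gy on study completed IMRT to 70 Gy off of study".

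**Definition used for PFS censoring (SAP 5.2.6).** "The start date of new anti-cancer therapy is the earliest date after randomization amongst the following": drug therapy on the follow-up page, radiotherapy ("Start date of radiation therapy recorded in ‘Follow-up Radiation Therapy’ eCRF pages with ‘Treatment Intent’ = ‘Curative in intent"), or resecting surgery. There is no exception for completing the assigned course.

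**Definition used for the safety window (SAP 5.2.5).** This is a separate, drug-only definition: the "earliest start date of anti-cancer drug therapy recorded in the ‘Follow-up Cancer Therapy’ eCRF pages" after the first study dose. Under SAP 5.2.7 the on-treatment period ends at the earlier of 30 days after the last study dose and the day before that drug starts. SAP 3.4.1 makes IMRT a study drug.

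**Censoring.** Tables 12 (M1, M1_B) and 14 (S1) have a row "New anti-cancer therapy given". Table 12 censors at the last adequate tumor assessment or clinical evaluation before the new therapy. Table 14 accepts tumor assessments only.

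**Assessment schedule (SAP 2.2).** The first post-baseline assessment is "12 weeks after the completion of CRT (ie, 10 weeks following completion of the CRT Phase of the study").

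**AE reporting (protocol 8.2).** When a new anticancer therapy begins, "the AE reporting period for non-serious AEs ends at the time the new treatment is started".

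**The concern.** Eligibility requires candidates for definitive CRT with curative intent, so the curative-intent filter in 5.2.6 picks up exactly the remaining fractions of the planned course. Those fractions are not a change of treatment strategy. The protocol treats other parts of the initial plan differently: a neck dissection within 140 days of CRT belongs to initial treatment, and 70 Gy is a completed dose whatever the delays.

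M1 and S1 are the checks of whether the PFS result is robust to new therapy, and M1_B is one of the BICR analyses added at FDA request. Under the rules as written they could drop patients who changed only the setting of their CRT. On the safety side, non-serious AEs that are never recorded cannot be recovered at analysis.

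**Working it through.** **1. The plan's own figure.** The target is 289 PFS events (one-sided 0.025, 90% power, HR 0.68). The Schoenfeld formula gives 283 and the Freedman formula 290. A two-look Lan-DeMets O'Brien-Fleming calculation at 217/289 gives interim alpha 0.0097, z = 2.338, final p = 0.0221 and power 0.902. The figure is reproduced and is not in dispute.

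**2. Calendar, in days from randomization.** Inputs: first dose 0 to 3 days after randomization, CRT Day 1 seven days later, 35 fractions Monday to Friday.
- CRT Day 1: 0 + 7 to 3 + 7 = day 7 to 10.
- Last fraction, 46 days later: day 53 to 56.
- First scheduled post-baseline assessment: + 84 = day 137 to 140, or week 19.6 to 20.0.
- Second: + 112 = day 249 to 252, or week 35.6 to 36.0.

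Therapy labelled as new during CRT therefore comes before every scheduled post-baseline scan.

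**3. Censoring date by analysis.**
- *S1:* randomization, barring an unscheduled or withdrawal scan. Footnote 2 of the maintenance schedule limits withdrawal imaging to patients who stop early and refuse follow-up.
- *M1, M1_B:* randomization, unless a clinical evaluation counts. Physical examinations are scheduled on CRT Days 8, 25 and 39. The SAP does not define a qualifying evaluation, and protocol 3.2 ties tumor clinical evaluations to the scan schedule. If Day 39 counted, censoring would fall at 7 + 38 to 10 + 38 = day 45 to 48, about week 7.
- *Early events:* both tables count PD or death within 36 weeks of randomization as an event and do not rank that row against the new-therapy row. The outcome is undetermined.

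**4. Safety window.** Radiotherapy alone does not cut it. The documented patient had 40/2 = 20 fractions, leaving 15, or 3 weeks = 21 days, inside the 30-day tail if treatment resumed promptly. With no breaks, 22 remaining fractions take 30 days, so radiotherapy outlasts the tail only if the patient leaves before about 26 Gy.

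A follow-up-page drug does cut it. As an illustration (the documents do not report this for any patient), suppose the last study dose is fraction 20 on CRT Day 26, taking Day 1 as a Monday. The window would run to Day 26 + 30 = 56. Off-protocol cisplatin recorded on Day 43 would end it on Day 42, 14 days sooner.

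**5. Size.** The number affected is not given. Assuming a fraction f of 640 with proportional loss of events, retained events are 289 × (1 − f). Nominal power is Φ(−ln 0.68 × √(events/4) − 1.96).

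| f | Patients | Events kept | Nominal power |
|---|---|---|---|
| 1% | 6 | 286 | 0.903 |
| 3% | 19 | 280 | 0.898 |
| 5% | 32 | 275 | 0.892 |
| 10% | 64 | 260 | 0.875 |

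For bias, assume exponential PFS, a 33-month control median, HR 0.80 apart from the leavers, 36 months' follow-up, and leavers at 2 to 3 times their arm's hazard. The HR is the ratio of events per person-time; dropping the leavers gives 0.80.

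| Leavers, Arm A / Arm B | HR, all patients |
|---|---|
| 5% / 2% | 0.82 to 0.83 |
| 8% / 4% | 0.83 to 0.84 |
| 3% / 3% | 0.80 |

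**The case against.** The strongest reply is that little of consequence is touched. Primary PFS counts events regardless of later therapy, M1, S1 and M1_B are labelled purely exploratory, and the other BICR analysis, S0_B, uses Table 13, which has no new-therapy censoring. SAE reporting runs 90 days after last dose, the irAE window runs 90 days regardless of new drug therapy, and AEs collected outside the on-treatment period are still listed. All of this stands and limits the weight of the point.

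It also stands that the classification depends on data entry the documents do not describe. IMRT data are non-CRF, and IMRT days and compliance are assessed by a central vendor. Against that, SAP 6.5.5 draws therapy after discontinuation from the same follow-up pages, and inconsistent site practice would itself call for a rule.

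Three stronger readings are tempting but unsupported:
- *All three analyses censor at randomization.* Table 12 also accepts clinical evaluations, so this is not fixed for M1 and M1_B.
- *The treatment-emergent window always closes mid-CRT.* Only a follow-up-page drug does that; the radiotherapy limb of 5.2.6 does not govern the window.
- *The rule flatters avelumab.* Nothing shows more leavers in Arm A or toxicity as the usual reason. Protocol 1.2.2 covers 78 randomized patients, is not split by arm and gives no count of leavers; its one stated reason for stopping all therapy is personal. Protocol 6.4 says cisplatin intolerance or radiotherapy delay for toxicity neither requires nor suggests withdrawal.

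**Conclusion.** The gap is real and worth correcting. As written, SAP 5.2.5 and 5.2.6 can treat completion of the assigned CRT as new therapy. Provided it is recorded on the follow-up pages, S1 loses these patients at day 0, barring an extra scan. M1 and M1_B lose them at day 0 or, at latest, at an evaluation during CRT. The handling of their events within 36 weeks is undefined. Off-protocol cisplatin or another follow-up-page drug shortens the treatment-emergent window, and protocol 8.2, which is not limited to drugs, can end non-serious AE recording even when only radiotherapy continues.

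The loss of precision is small under any plausible count: nominal power stays at 0.875 or above with up to 10% affected. The hazard-ratio shift of about 0.02 to 0.04 requires an assumed arm imbalance and an assumed excess hazard, and is near zero with equal losses. No confirmatory result changes. Uncollected non-serious AEs are the part that cannot be repaired later.

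**What to change.** - In SAP 5.2.5, SAP 5.2.6 and protocol 8.2, state that radiotherapy or cisplatin given off protocol to complete the initial planned CRT, before any PD per modified RECIST, is not new anti-cancer therapy. The exemption then carries through to Tables 12 and 14, M1_B, the on-treatment period and AE recording.
- In Tables 12 and 14, rank the PD-or-death row against the new-therapy row.
- State which clinical evaluations qualify for censoring in Table 12, in particular whether examinations during CRT do.
- List the affected patients, blind to arm, before database lock.

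The cost is a few sentences in the SAP, one clarifying sentence in the protocol and one listing. The downside is small: a few records need blinded review of treatment intent, and slightly more AEs are recorded.
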